### 10.2.3 General Disorders (Fatigue and Asthenia)

Fatigue has been reported in 33.6% of subjects who received neratinib as monotherapy. The majority of fatigue AEs was reported as Grade 1 (19.1%), Grade 2 (11.6%), and Grade 3 (2.9%); none were Grade 4 or 5.

Asthenia has been reported in 14.3% of subjects who received neratinib as monotherapy, and the majority of those AEs were reported as Grade 1 (7.4%) and Grade 2 (4.8%).

### 10.2.4 Metabolic and Nutritional Disorders (Decreased Appetite and Dehydration)

Many forms of cancer present with a complex metabolic profile characterized by loss of lean body mass known as cancer cachexia. Decreased appetite characteristic of cancer cachexia is common in subjects with cancer. Approximately half of all subjects with cancer experience cachexia with prevalence as high as 86% [87].

Decreased appetite has been reported in 30.3% of subjects who received neratinib as monotherapy. Dehydration as a complication of diarrhea has been reported in 10.9% of subjects on neratinib monotherapy, in particular, when diarrhea is associated with nausea and vomiting. The vast majority of these events were  $\leq$ Grade 2 (7.1%).

### 10.2.5 Nervous System Disorders (Headache)

Headache is one of the more common side effects of TKIs reported in as much as 37% of subjects treated with imatinib and nilotinib[88] [89]. Headache has been reported in 17.9% of subjects who received neratinib as monotherapy. The majority of headache AEs was Grade 1 (14.3%), and the majority was reported as non-serious.

### 10.2.6 Hematologic Toxicities

Overall, hematologic toxicities have been reported in 20.6% of subjects who received neratinib as monotherapy. It is subdivided into 3 categories: anemia, leukopenia and neutropenia, and thrombocytopenia. Leukopenic and neutropenic events have been reported in 10.3% of subjects who received neratinib as monotherapy. The vast majority of the reports were  $\leq$ Grade 2 (8.8%). Specific event terms reported included lymphopenia (4.6%), leukopenia (3.2%), neutropenia (3.2%), WBC count decreased (1.5%), febrile neutropenia (0.2%), and neutrophil count decreased (0.2%). Thrombocytopenia has been reported in 1.7% of subjects who received neratinib as monotherapy.

Neratinib preclinical data from a 1-month and a 6-month toxicity study in rats showed decreases in parameters of red cell mass (RBCs, hemoglobin, and hematocrit, 4% to 9%). In the clinical setting, 19.1% of subjects on neratinib monotherapy presented treatment-emergent blood and lymphatic disorders, of which, 3.3% comprised Grade 3 and 4 events (there were no Grade 5 events). The most frequently reported event was anemia (10.9%), the majority of which were Grade 1 (5.7%) and Grade 2 (4%), with 1.3% of subjects reporting Grade 3/4. In addition, decreased hemoglobin has been reported in 3.8% of subjects who received neratinib monotherapy, the majority of which were Grade 1 (2.3%) and Grade 2 (1.3%).

### 10.2.7 Hepatotoxicity

In general, hepatotoxicity events have been reported in 18.1% of subjects who received neratinib as monotherapy. Specific event terms reported included ALT increased (8%), AST increased (8%), blood alkaline phosphatase increased (6.9%), gamma-glutamyl transferase (GGT) increased (3.4%), hypoalbuminaemia (2.3%), hyperbilirubinaemia (1.7%), ascites (0.8%), transaminases increased (0.8%), blood bilirubin increased (0.4%), hepatic failure (0.2%), hepatic function abnormal (0.2%), hepatic pain (0.2%), jaundice (0.2%), and varices oesophageal (0.2%). The vast majority of these events were  $\leq$ Grade 2 (12.8%) with a few Grade 3 (4.8%) and 1 subject (0.2%) who had Grade 4 events.

### 10.2.8 Pulmonary Toxicity

Dyspnea has been reported in 16.8% of subjects who received neratinib as monotherapy, the majority of which were Grade 1 (6.1%) and Grade 2 (4.4%). Uncommon reports of lung infiltration (0.2%) and pneumonitis (0.2%) have been received in subjects treated with neratinib as monotherapy. Both events were reported as Grade 1. Patients receiving neratinib should be monitored for acute onset or worsening of pulmonary symptoms such as dyspnea, cough, and fever, and treated appropriately.

### 10.2.9 Cardiac Toxicities

Overall, cardiac toxicities have been reported in 12.6% of subjects who received neratinib monotherapy. Cardiac toxicities are divided into 3 categories: cardiac arrhythmia, cardiac failure, and ischemic heart diseases.

**Cardiac Arrhythmia** events have been reported in 3.6% of subjects who received neratinib monotherapy. The majority of the events were  $\leq$ Grade 2 (3.1%). Specific event terms reported included palpitations (1.1%), tachycardia (0.8%), arrhythmia (0.6%), syncope (0.6%), loss of consciousness (0.4%), bradycardia (0.2%), and electrocardiogram abnormal (0.2%) (Data provided thorough Neratinib IB).

**Cardiac Failure** events have been reported in 6.9% of subjects who received neratinib as monotherapy. Specific events reported included oedema peripheral (4.6%), oedema (1.1%), ejection fraction decreased (0.6%), left ventricular dysfunction (0.4%), cardiac failure (0.2%), and cardiopulmonary failure (0.2%). The majority of the reports were  $\leq$ Grade 2 (6.6%) (**Table 13**). Guidelines for dose adjustments of neratinib in the event of abnormalities in LVEF are provided in study protocols, which include withholding treatment if LVEF is below 50% and discontinuation of treatment for symptomatic cardiac failure. Subjects receiving neratinib should be monitored for the development of signs and symptoms of congestive heart failure and evaluated appropriately.

**Ischemic Heart Disease** events have been reported in 3.8% of subjects who received neratinib as monotherapy. Specific event terms reported included blood creatine phosphokinase increased (1.9%), electrocardiogram T wave abnormal (0.4%), coronary artery stenosis (0.2%), electrocardiogram T wave inversion (0.2%), troponin I increased (0.2%), and troponin increased (0.2%). The majority of these events are  $\leq$ Grade 2. Four (4) cases of angina pectoris (0.8%) have been observed in subjects on neratinib monotherapy; all cases were  $\leq$ Grade 2 and were non-serious. In addition, 1 non-serious Grade 2 subendocardial ischemia and 1 serious Grade 4 acute myocardial ischaemia have also been reported (Neratinib IB).

**Table 13. Summary of LVEF Abnormalities, Shift from Baseline in % by Worst On-study Value, Occurring in Subjects With Advanced Solid Malignancies Receiving Single-agent Neratinib (240 mg, All Subjects, Safety Population, Pooled Studies)**

Baseline LVEF	Number of Subjects (N =476) Worst LVEF% On-Study			
	<45% n (%)	45%-50% n (%)	50–55% n (%)	≥55% n (%)
<45%	0	0	0	0
45-50%	0	0	3 (0.6)	0
50-55%	1 (0.2)	4 (0.8)	14 (2.9)	9 (1.9)
≥55%	5 (1.1)	3 (0.6)	35 (7.4)	299 (62.8)

## 11.0 Correlative/Special Studies

### 11.1 PK Analysis

A population pharmacokinetic-pharmacodynamic analysis of neratinib efficacy and tolerability endpoints will be performed in this patient population to assess the variability of neratinib concentrations among individuals in the target patient population. Blood samples will be collected, processed and stored until analysis.

PK samples will be collected at the following time points: Cycle 1 Day 15 pre-dose ( $\pm$  20minutes), 6 hours post-dose (60 minutes) and Day 1 Cycle 3 and Day 1 Cycle 4 pre-dose ( $\pm$  20 minute) (Table 14). All pre-dose samples should be collected within 30 minutes before the daily dose. Patients will be instructed to record the exact time to the minute that the dose was taken on these days. In the event that the neratinib dose is held or the dose level is changed, pharmacokinetic sample will be rescheduled accordingly.

**Table 14. PK Sample Collection Time Points**

PK sample collection	Cycle 1 Day 15 ( $\pm$ 1day)	Cycle 3 Day 1 ( $\pm$ 3days)	Cycle 4 Day 1 ( $\pm$ 3days)
Collection time	Pre-dose ( $\pm$ 20 minutes); 6 hours post-dose ( $\pm$ 60 minutes)	pre-dose ( $\pm$ 20 minutes).	Pre-dose ( $\pm$ 20 minutes).

At each of the required time points, 10 mL venous blood will be collected into a tube containing K2EDTA. Samples will be inverted several times and kept on ice until processing can begin. Plasma will be separated from whole blood by centrifugation at 1,500 x g for 10 minutes at 4° C and ten approximately equal aliquots (300 uL minimum) will be transferred to appropriately-labeled polypropylene tubes and maintained on wet ice until frozen at  $\leq$  -70°C until shipping. Specimens will be batched at each participating site and stored in freezers at each site. At City of Hope, the specimens will be stored in a freezer accessible only to members of the City of Hope pharmacokinetic staff working under the auspices of [name]. Each tube will be labeled with the study number, patient registration number, time point, and the date and time the sample was drawn.

At end of study, a shipment of frozen serum samples at each site will be packed in the shipping container in sufficient dry ice to last at least 3 days (typically 6-8 kg). The container will be sealed and shipped along with the packing worksheet via courier to:

Covance Bioanalytical  
 [name]  
 Madison, Wisconsin 53704-2523;  
 [contact]

Concentrations of neratinib will be measured in plasma with a validated assay method.

NONMEM, a statistical software program that uses non-linear, mixed effects models to determine PK parameters (clearance and volume of distribution), the inter- and intra-patient variability and the population variability in the parameter estimates will be used for this analysis. Random sources of error, intrinsic factors (e.g., age, sex, race, body weight, liver function and renal function) and extrinsic factors (e.g., concomitant medications such as proton pump inhibitors, digoxin, or anti-infectives) will be evaluated to identify factors that contribute to the observed variability in the PK parameter estimates.

A population pharmacokinetic-pharmacodynamic analysis of neratinib efficacy and tolerability endpoints will be performed in this patient population. The final PK data will be used to generate post-hoc neratinib patient-level plasma PK profiles, from which patient-level neratinib area under the curve (AUC) and maximum plasma concentration (Cmax) exposure metrics will be estimated. Neratinib dose and estimated AUC and Cmax exposure metrics will then be used to complete an exploratory data analysis of potential exposure-response relationships for efficacy and safety endpoints.

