
Limited evidence exists to guide therapy with targeted agents in the older adult because these patients have been under-represented in clinical trials. Adults age 70 and older make up only 20% of subjects enrolled in FDA registration trials, but 46% of all patients with cancer are older adults. Dose-finding studies specifically in older adults are not routinely performed despite changes in drug metabolism, absorption, and distribution with increasing age.
 
Neratinib is a potent oral small molecule that inhibits HER1, HER2 and HER4 at the intracellular tyrosine kinase domains through irreversible binding at a targeted cysteine residue in the ATP binding pocket of the receptor. Both the ability of neratinib to concurrently block signal transduction through the three active tyrosine kinase HER receptors, and its irreversible binding and prolonged inhibition of these growth-promoting pathways, provide the opportunity to further improve the clinical benefit of its use in HER2+ MBC patients. Early clinical data have demonstrated the activity of neratinib in patients who have already progressed through treatment with other small molecule or antibody-based HER2 targeted therapies. With the promising results from multiple clinical trials, neratinib has the potential to emerge as a novel therapy for patients with HER2 positive breast cancer. There is significant interest in studying this drug among older adults, as it is a targeted therapy which is convenient to prescribe and easy to administer. However, there is a significant amount of GI toxicity. In particular, grades 1-4 diarrhea occurred in 92% of patients. Grade 3-4 diarrhea occurred in over 30% of patients and dose reductions secondary to diarrhea range from 20-53% across 9 trials of neratinib alone or in combination with other therapy [1-9]. This particular side effect is likely to be significant in the population of older adults who are particularly vulnerable to diarrhea. Currently, there are 6 trials of neratinib therapy with a total enrollment of 291 patients, but only 38 patients are 65 and older (data provided by PUMA). Therefore, there is a significant gap of knowledge regarding the toxicity profile of neratinib in older adults, as well as the optimal supportive care medications to minimize side effects.

Objectives:
Primary Objective:

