#### **6.4 Dose Assignment**

Study patients will receive the same initial dose of study agents (see **Section 7.0**). Dose reductions can occur if medically necessary as described below (see **Section 8**).

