##### **7.1.1 Neratinib**

**7.2 Neratinib investigational product will be supplied as 40 mg film-coated tablets packaged in bottles with desiccant. Neratinib (240 mg initial dose; provided as six 40 mg tablets) will be self-administered orally by patients on a daily basis, starting with Cycle 1/Day 1. Neratinib must be taken with food, in the morning. Neratinib is to be taken continuously in 28-day cycles, with no rest between cycles. Doses missed for toxicity will not be made up. Dose Adjustment**

Management and dose modification associated with adverse events are outlined in **Section 8**.

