### 7.6.1 Required Concomitant Treatment

#### 7.6.1.1 Loperamide Antidiarrheal Therapy

Diarrhea is the major dose-limiting toxicity of neratinib with onset typically occurring early in the course of treatment (during the first few weeks). Primary prophylactic use of antidiarrheal medication is **mandatory** for all enrolled patients in the neratinib study.

Loperamide is the recommended standard therapy to treat diarrhea in this study. If alternative antidiarrheal medication is proposed, this should be discussed with the PI and the reason documented in the source documents. Second-line antidiarrheal treatments and adjunctive

therapies (i.e., octreotide [SANDOSTATIN®]) (or equivalent as approved by the PI) are also recommended for use when appropriate.

All patients are required to receive intensive diarrhea prophylaxis:

- For the first 14 days, loperamide 4 mg (2 tablets/capsules) will be self-administered orally by patients 3 times a day (total 12 mg a day). The initial dose of loperamide 4 mg will be self-administered orally with the first dose of neratinib.
- After the first 14 days, loperamide 4 mg (2 tablets/capsules) will be self-administered orally twice a day (total 8 mg a day) through the first cycle of therapy (Day 28) from start of neratinib dosing.
- Thereafter, loperamide will be administered as needed (not to exceed 16 mg per day). The goal is to titrate to 1-2 bowel movements a day. Recommended loperamide dosing is listed below in **Table 5**.

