## **8.0 Dose Delays/Modifications for Adverse Events**

---

Patients will be treated per protocol or until disease progression or withdrawal from treatment due to unacceptable adverse events or treatment consent withdrawal. At each study assessment, subjects are to be evaluated for evidence of drug-related adverse events.

In all cases where the subject is withdrawn due to unusual or unusually severe adverse event considered related to neratinib, the Investigator must report the withdrawal as a Serious Adverse Event.

Treatment may be delayed for up to 4 weeks, to allow for resolution of toxicity except in the event of those toxicities described below in which cases treatment must be discontinued permanently (see **Table 7**).

Recommended dose reductions for the -1 and -2 dose levels of Neratinib are listed as following:

Dose level	Neratinib
Starting dose	240mg
-1	160mg
-2	120mg

If a dose of neratinib is held, study procedures for that cycle will proceed on schedule as planned, without any delay. This also applies to tumor assessments, which should continue to be done every 12 weeks, starting from the first dose of neratinib until the first planned tumor assessment at 12 weeks ( $\pm 1$  wk), and then after every subsequent 12 weeks ( $\pm 1$  week) of treatment regardless of any changes in dose or occurrence of AEs. Missed dose(s) of neratinib (i.e., any

dose that is not administered within the protocol-defined administration window) will not be made up. The dose adjustment guidelines represent the minimum set of measures that investigators must follow. However, additional measures may be taken as necessary, for certain patients per the Investigator's medical judgment. All dose modifications/adjustments should be documented in the patient's source file.

Once neratinib dose has been reduced for a patient, all subsequent cycles must be administered at that dose, unless further dose reduction is required. Dose re-escalation is not permitted.

If a patient developed AE requiring dose reduction while on neratinib dose level of 120mg, neratinib will be discontinued.

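### Section 11.1 relates neratinib dose, AUC and Cmax to safety without fixing exposure before the event, so toxicity-driven dose reductions can bias the result toward lower exposure with more toxicity

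*Combined protocol and SAP*

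**What the plan says.** Section 11.1 plans a NONMEM population model that estimates clearance and volume. Post-hoc individual profiles from it supply patient-level AUC and Cmax. Then: "Neratinib dose and estimated AUC and Cmax exposure metrics will then be used to complete an exploratory data analysis" of possible exposure-response relationships for efficacy and safety endpoints. Section 3.2 lists exposure-response on efficacy and safety among the secondary endpoints, and Section 15.3 repeats the aim. Neither 11.1 nor 15.3 says whether exposure means the starting dose, the dose in force at sampling, a time average, or exposure before the event.

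The dosing rules leave little room for dose to vary for other reasons:
- Section 6.4: "Study patients will receive the same initial dose of study agents". Section 7.1.1 sets that dose at 240 mg.
- Section 8.0 gives 160 mg and 120 mg as the reduced levels and adds: "Dose re-escalation is not permitted".
- Tables 7 and 8 tie reductions to adverse reactions, mainly Grade 3 or higher. Table 7 excludes unrelated Grade 2 or 3 events.
- Section 7.6.1.1: "Diarrhea is the major dose-limiting toxicity of neratinib with onset typically occurring early in the course of treatment".
- PK samples are taken at Cycle 1 Day 15 (two samples), Cycle 3 Day 1 and Cycle 4 Day 1. Section 11.1 adds: "In the event that the neratinib dose is held or the dose level is changed, pharmacokinetic sample will be rescheduled accordingly".

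**The concern.** An exposure-safety analysis needs an exposure that comes before the outcome. Assigned dose is the same for every patient and cannot explain differences between them. The neratinib dose that varies within this trial is the received dose, and under the protocol rules it falls because of toxicity. Regressing toxicity on it runs the arrow backwards. AUC and Cmax have the same fault if they are computed at the received dose, and nothing in the plan requires otherwise.

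The result at risk is a listed secondary endpoint. Sections 1.1 and 1.7 give as part of the rationale that oncologists may reduce the dose in older adults without guidance. A finding that patients with lower exposure had more toxicity, or that exposure hardly matters, would be easy to misread in that setting.

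**Working it through.** **The plan's own figures.** The plan gives no precision figure for the exposure-response analysis. Its general figures for n=40 (Section 15.1) reproduce and are not disputed: maximum 95% half-width 0.162 (stated 0.16), 8/40 gives 0.091 to 0.356, and P(at least one event at a true rate of 0.05) = 0.871.

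**Inputs from the documents.** n=40; start 240 mg; reduced levels 160 and 120 mg; Grade 3-4 diarrhea under prophylaxis 12-16% (Section 1.4.5.5), or 4.8 to 6.4 of 40 patients.

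**Assumed, because the documents do not give them.** Between-patient CV of AUC; Grade 2+ rate of 60%; share of patients reduced; share of reductions that precede sampling.

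**Step 1, dose as predictor.** If Grade 3+ toxicity is the endpoint and the only trigger, P(toxicity | reduced) = 1.00 and P(toxicity | not reduced) = 0.00 by construction. For Grade 2+ at 60% with 20% of patients reduced, the values are 1.00 and (0.60 - 0.20)/(1 - 0.20) = 0.50. Lower dose goes with more toxicity whatever the pharmacology.

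**Step 2, size of the shift in AUC at the received dose.** ln(160/240) = -0.405, so AUC is 33% lower. The SD of log AUC is sqrt(ln(1 + CV²)): 0.385 at CV 40% and 0.555 at CV 60%.

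**Step 3, false inverse association under the null.** AUC at 240 mg is log-normal and independent of toxicity; AUC is multiplied by 160/240 in reduced patients; the test is a two-sample t-test on log AUC, counting two-sided p<0.05 in the inverse direction.

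| Setting (CV 40-60%) | Share of trials |
|---|---|
| Grade 3+ at 12-16%, all reductions before sampling | about 29-64% |
| Grade 3+ at 12-16%, half before sampling | about 12-23% |
| Grade 2+ at 60%, 15-20% of patients reduced | about 8-16% |
| AUC predicted at 240 mg for everyone | about 2.4% |
| Chance in that direction | 2.5% |

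Hand check of the first row, with t critical value 2.024 on 38 df:
- 16%, CV 40%: SE = 0.385 × sqrt(1/6.4 + 1/33.6) = 0.166; 0.405/0.166 = 2.44; Φ(2.44 - 2.02) ≈ 0.66.
- 12%, CV 60%: SE = 0.555 × sqrt(1/4.8 + 1/35.2) = 0.270; 0.405/0.270 = 1.50; Φ(1.50 - 2.02) ≈ 0.30.

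**Step 4, when there is a true effect.** Logistic slope of toxicity on log AUC at the final dose, in 200,000 simulated patients, with 25% of reduced patients going on to 120 mg (assumed):

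| Endpoint | True slope | CV 30% | CV 50% | CV 80% |
|---|---|---|---|---|
| Grade 3+, 15% | 0 | -5.2 | -2.1 | -0.95 |
| | 1 | -4.3 | -1.2 | -0.03 |
| | 2 | -3.6 | -0.4 | +0.7 |
| Grade 2+, 60%, one third reduced | 0 | -1.3 | -0.6 | -0.3 |
| | 1 | -0.6 | +0.2 | +0.6 |
| | 2 | 0.0 | +1.0 | +1.4 |

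The bias is downward in every cell. The sign reverses in some; in others the slope is only attenuated. With AUC at the starting dose, true slopes of 0, 1 and 2 are recovered as about 0.00, 0.99-1.00 and 1.98-2.00.

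**The case against.** The strongest reply is that the plan never says AUC and Cmax are taken at the reduced dose. NONMEM estimates individual clearance allowing for the dose given, so a sample drawn at 160 mg does not itself bias it, and AUC at 240 mg would fit the present wording. That stands: for AUC and Cmax the defect is a missing definition. It does not rescue dose, which 11.1 names as a metric and which has no useful variation in this trial except as received dose. Section 15.3 does place the samples in a population PK dataset. If that includes other studies, dose may vary for other reasons, but the documents do not say.

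A reader might infer that most samples follow a reduction. The documents do not establish this: two of the four are at Cycle 1 Day 15, and the rescheduling sentence does not say at which dose the new sample is drawn.

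A reader might also take the synopsis figure, "dose reductions secondary to diarrhea range from 20-53% across 9 trials of neratinib", as the expected reduction rate. With 20-53% of patients reduced and every toxicity patient reduced before sampling, the false inverse rate is 42-89% at 160 mg and 84-100% at 120 mg. Those trials gave neratinib alone or in combination, and Section 1.4.5.5 says earlier trials did not mandate prophylaxis. Here it is mandatory, and most Grade 2 events trigger no reduction. The figure is a worst case.

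Patient-initiated reductions are also recorded (synopsis), so received dose is not purely a marker of toxicity. Finally, the analysis is labelled exploratory and has no decision rule. That limits the stakes but does not remove the bias.

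**Conclusion.** The point holds for safety endpoints. Received dose should not be used to predict the toxicity that lowered it, and AUC and Cmax need a stated reference dose or time window. The direction of the bias is certain if received-dose exposure is used. Its size is not: about 29-64%, 12-23% or 8-16% false inverse findings under the null, depending on endpoint and timing, given an assumed CV of 40-60% and reduction to 160 mg.

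It would go too far to say that the analysis will show the wrong sign, or that the plan does use toxicity-lowered AUC. The first depends on variability, endpoint and true effect; the second is one reading of an undefined term. Nor do these results support a claim about the efficacy relationship, where time on drug raises separate questions. The primary toxicity estimate is unaffected.

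**What to change.** In Sections 11.1 and 15.3, state that for safety endpoints:
- received dose is not used as a predictor;
- AUC and Cmax are predicted at the 240 mg starting dose from each patient's individual CL/F (AUC = 240/(CL/F)), or exposure is restricted to the time up to the first event;
- received dose, and AUC at the received dose, are reported descriptively only.

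This takes a sentence or two and a different output from the same NONMEM fit. It needs no new samples, visits or patients, and no dosing rule changes. The small downside is reliance on individual CL/F estimates from four samples, which the plan already needs.
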